2.6.1. Costs to Provider (HIV Diagnostic Assistant)

Costs will be measured from the perspective of the HDA (the "provider" of HIV testing). We will use micro-costing methods to estimate the cost of HIV testing in each study arm.^{25, 26, 27} We

will first create an inventory of all the resources used to achieve the observed study outcomes. Resources to be captured will include:

- HIV self-test kits
- Standard of care HIV testing supplies - Determine and Uni-Gold test kits
- Other services provided (e.g. counseling interactions)
- Fixed costs of patient care (building space, equipment, human resources)

For each study patient, the quantity (number of units) of resources used will be determined. Unit costs of resources, which are not human subjects data, will be obtained from external suppliers and the site's finance and procurement records and multiplied by the resource usage data to provide an average cost per study patient across centers in each study arm. Costs will be reported as means (standard deviations) and medians (IQRs) in U.S. dollars, using the exchange rate prevailing during the follow-up period.

2.6.2. Cost-Effectiveness

Using the average cost per patient as described above, we will then estimate the cost per outcome achieved in each arm. Two measures of effectiveness will be utilized for the cost-effectiveness analysis: the proportion of individuals tested for HIV and the cost per HIV-positive individual identified. We will calculate the difference in cost divided by the difference in effectiveness between study arms for both measures of effectiveness.

The price of the self-test (if self-testing were to become widely available in Malawi) is currently uncertain. As such, we will conduct a sensitivity analysis where all costs and outcomes remain constant, and the price of self-tests alone is varied. This analysis will then provide a plausible range of the cost-effectiveness of self-testing.

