2. AIM 1: GROUP SELF-TESTING

2.1. OBJECTIVES

2.1.1. Primary Objectives:

- To determine whether group self-testing in waiting areas of outpatient departments (OPD) and sexually transmitted infection (STI) clinics is superior in regard to number tested compared to optimized standard of care (provider-initiated-testing-and-counseling; PITC)
- To determine whether group self-testing in waiting areas of OPD and STI clinics is cost-effective compared to optimized standard of care using PITC

2.1.2. Secondary Objectives:

- To assess the acceptability of self-testing in waiting areas of OPD and STI clinics
- To determine whether group self-testing in waiting areas of OPD and STI clinics is superior in regard to number of HIV+ individuals identified (testing yield)
- To determine whether group self-testing in waiting areas of OPD and STI clinics is superior in regard to linkage rates for those who identify as HIV-positive compared to standard of care and optimized standard of care (PITC)

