2.5. STATISTICAL METHODS

2.5.1. Outcome Measures

Power Calculations and Statistical Analysis for Primary Outcome Measures

We have 15 clusters available for randomization, and therefore, estimated our sample size assuming a fixed number of clusters (k) and an equal number of clusters per arm (k=5). We also assumed an equal number of participants per cluster (n=1,000) for a total sample size of 5,000 participant per arm (15,000 total). Assuming a type I error of 0.05, an intra-cluster correlation of 0.004, we would expect at least 95% power to detect study arm testing coverage of 5% in study arm 1, at least 10% in study arm 2, and 60% in study arm 3.

We will calculate descriptive statistics, including mean/median, variation (standard deviation, kurtosis), range, and frequency distributions for the demographic and clinical characteristics, overall and by study arm. The outcomes of interest include the proportion of participants tested and HIV-positivity among those tested. Differences in the prevalence of each of the outcomes of interest will be examined by study arm as well as by other factors of interest including demographic characteristics (e.g., age, gender), clinical characteristics (e.g., reason for clinic visit), and structural factors (e.g., geographic location). The differences will be evaluated using t-tests, Mann-Whitney U test (or other non-parametric tests), chi-square methods, and Fisher's exact test as appropriate. In order to assess factors associated with HIV testing/positivity, we will use hierarchical linear models in order to account for clustering of effects within each clinic. Separate models will be developed for each outcome of interest and covariates of interest include patient characteristics (e.g., age, gender) and other structural and contextual factors.

Qualitative Analysis for Secondary Outcome Measures

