2.6. COST AND COST-EFFECTIVENESS METHODS

It is expected that group self-testing will be cost-effective compared to standard of care and optimized standard of care for HIV testing. For facilities, fewer HDA staff would be needed to achieve testing coverage, and it is possible that more positives will be identified. The study will estimate differences in overall costs for both standard of care arms and group self-testing. Costs of HIV testing will be estimated as the average cost per individual who completes an HIV test.

Using the average cost per patient tested we will estimate the cost for identifying each HIV-positive individual. We will compare average cost per HIV-positive individual identified among the three study arms with the primary comparison of optimized standard of care compared to group self-testing. To provide information for HIV program budgets, we will also estimate the annual cost of providing HIV testing at a site under the three strategies evaluated, independent of outcomes.

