6.2. Cost-Effectiveness

Using the average cost per patient as described above, we will then estimate the cost per outcome achieved in each arm. The main measure of effectiveness for the cost-effectiveness analysis will be both the primary study outcome of proportion of partners tested as well as yield (newly identified HIV-positive partners of index cases). We will calculate the difference in cost divided by the difference in effectiveness among study arms for both effectiveness measures.

The price of the self-test itself is currently uncertain because it is not widely available in Malawi. As such, we will conduct a sensitivity analysis where all costs and outcomes remain constant, and the price of self-tests alone is varied. This analysis will then provide a plausible range of the cost-effectiveness of partner self-testing.

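### Aim 1's second cost-effectiveness ratio uses a cost per case as its effectiveness measure, so cost sits in both numerator and denominator

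*Combined protocol and SAP*

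**What the plan says.** Cost-effectiveness against optimized standard of care is one of the two Aim 1 primary objectives (section 2.1.1). Section 2.6.2 sets out how it will be assessed. It begins "Two measures of effectiveness will be utilized for the cost-effectiveness analysis" and names them as "the proportion of individuals tested for HIV and the cost per HIV-positive individual identified". It then instructs: "We will calculate the difference in cost divided by the difference in effectiveness between study arms for both measures of effectiveness". For the uncertain kit price it adds that "we will conduct a sensitivity analysis where all costs and outcomes remain constant, and the price of self-tests alone is varied".

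Three other places bear on the meaning:

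- Section 2.6 derives the cost of finding one positive from the average cost per patient tested, and plans a plain comparison of the result: "We will compare average cost per HIV-positive individual identified among the three study arms", with self-testing against optimized standard of care as the main contrast.
- Section 2.1.2 lists the count of positives found (testing yield) as a secondary Aim 1 outcome.
- Section 6.2, the Aim 2 counterpart of 2.6.2, pairs the proportion of partners tested with yield, meaning newly found positive partners. Neither of those measures contains a cost.

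**The concern.** An incremental cost-effectiveness ratio needs a health or service outcome in its denominator. Here the second denominator is the difference between two costs per case, a quantity on which lower is better. The instruction applies the ratio explicitly to both measures, so the second item cannot be read as a stand-alone average.

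Section 2.6.2 is also at odds with itself. Its sensitivity analysis holds outcomes fixed while the kit price varies, yet an effectiveness measure built from cost must change when that price changes.

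What is at stake is the case-finding ratio for a primary objective. Followed literally, it can take a negative sign when self-testing costs more in total and less per case, which is a favourable finding. The price analysis can also point the wrong way.

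**Working it through.** The documents state no cost-effectiveness figure, so there is nothing to reproduce. The check is on units and algebra first, then an illustration.

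**Definitions.** Let C be cost per attendee (section 2.6.1 yields an average cost per study patient) and y be positives identified per attendee. Subscript 2 is optimized standard of care and subscript 3 is self-testing.

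- Ratio as written: W = (C3 - C2) / (C3/y3 - C2/y2)
- Ratio with an outcome in the denominator: R = (C3 - C2) / (y3 - y2)

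**What follows without any assumed figure.**

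1. Units of W are (USD per attendee) / (USD per positive) = positives per attendee. It is not a cost per outcome.
2. Multiplying all costs by k multiplies the top and bottom of W by k, so W does not change. R is multiplied by k, as it should be.
3. W is undefined when C3/y3 = C2/y2. It is negative when C3 > C2 but C3/y3 < C2/y2.
4. The derivative of W with respect to C3 has the sign of C2(1/y3 - 1/y2). If self-testing finds more positives per attendee (y3 > y2), this is negative. A dearer self-test then lowers W wherever W is defined, apart from the jump at the undefined point, while R rises.

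**Illustration.** Coverage is from section 2.5.1: "at least 10% in study arm 2, and 60% in study arm 3". The documents give no unit cost or positivity, so these are assumptions: USD 4 per optimized standard of care test, 5% positivity in both arms, and an all-in self-testing cost of USD 3 to 8 per test.

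Optimized standard of care: C2 = 0.10 x 4 = USD 0.40; y2 = 0.10 x 0.05 = 0.005; cost per positive 0.40/0.005 = USD 80. Self-testing: y3 = 0.60 x 0.05 = 0.030, so y3 - y2 = 0.025.

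| Self-test cost (USD) | C3 (USD) | Cost per positive (USD) | W as written | R (USD per additional positive) |
|---|---|---|---|---|
| 3 | 1.80 | 60 | 1.40/(60 - 80) = -0.070 | 1.40/0.025 = 56 |
| 4 | 2.40 | 80 | 2.00/0, undefined | 2.00/0.025 = 80 |
| 6 | 3.60 | 120 | 3.20/(120 - 80) = 0.080 | 3.20/0.025 = 128 |
| 8 | 4.80 | 160 | 4.40/(160 - 80) = 0.055 | 4.40/0.025 = 176 |

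**Varying the assumptions.**

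- Positivity 2% in both arms, USD 3: W = 1.40/(150 - 200) = -0.028; R = 1.40/0.010 = USD 140.
- Positivity 10% in both arms, USD 3: W = 1.40/(30 - 40) = -0.140; R = 1.40/0.050 = USD 28.
- Positivity 10% under optimized standard of care and 5% under self-testing, USD 3: W = 1.40/(60 - 40) = +0.070; R = 1.40/0.020 = USD 70. The sign is not reversed here.
- The same positivities at USD 6: W = 3.20/(120 - 40) = 0.040; R = 3.20/0.020 = USD 160. W again falls as R rises.
- Comparator test at USD 5, 5% positivity in both arms: W is -0.033, -0.095, undefined, 0.155 and 0.072 at self-test costs of USD 3, 4, 5, 6 and 8; R is USD 52, 76, 100, 124 and 172. The pattern is the same.

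**The first ratio** (proportion tested) is properly formed: at USD 3 it is 1.40/(0.60 - 0.10) = USD 2.80 per additional person tested.

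**The case against.** The strongest reply is that this is a slip of wording whose intent can be recovered. The sentence before it speaks of estimating a cost for each outcome achieved, and Aim 2 names yield, so the clause probably states the output where it meant the effect. An analyst would likely notice a negative or unitless ratio. Section 2.6 also already plans a valid comparison of average cost per positive. Most of this stands, and it limits the importance of the point. It does not remove the point. The incremental case-finding ratio has no usable prespecified definition, and the average is a different quantity: with 10% and 5% positivity at USD 3, the self-testing average is USD 60 while each additional positive costs USD 70.

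A second reply is that the numerator might be cost per person tested, as section 2.6 uses. With 5% positivity in both arms, the written ratio is then (3 - 4)/(60 - 80) = (6 - 4)/(120 - 80) = (8 - 4)/(160 - 80) = 0.05. There is no sign reversal and no movement with price. That is correct, and the negative and falling values above do depend on the per-attendee numerator. But section 2.6.2 refers back to the average cost per patient, which in 2.6.1 is per study patient, and the ratio on proportion tested needs a per-attendee cost too. On the alternative reading the ratio merely returns the assumed positivity. With 10% and 5% positivity it goes from (3 - 4)/(60 - 40) = -0.05 at USD 3 to (6 - 4)/(120 - 40) = 0.025 at USD 6. It is uninformative either way.

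Third, the dollar inputs are invented, and they treat all self-testing cost as one per-test figure, whereas section 2.6.1 also counts counselling, space, equipment and staff. That is fair: the individual values carry no weight as estimates. The units and rescaling arguments do not depend on them.

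**Conclusion.** The point holds. Read as written, the second Aim 1 ratio has cost in both halves, carries no monetary unit and cannot express value for money. No Aim 1 text corrects it. Under the stated assumptions it can be negative (-0.070 against USD 56), undefined (against USD 80), or falling while the true incremental cost rises (0.080 to 0.055 against USD 128 to USD 176). The sign does not reverse under every set of inputs.

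The damage is partial. The ratio on proportion tested and the section 2.6 comparison of average cost per positive remain valid, and randomization and the testing outcome are untouched. It should be fixed, because it leaves one of the two ratios planned for a primary objective without a meaningful definition, and the effect measure would otherwise have to be chosen later, possibly with data in hand.

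**What to change.** In section 2.6.2, replace the second effectiveness measure with *the number of HIV-positive individuals identified*, expressed per attendee when the numerator is cost per attendee. The ratio then becomes the incremental cost per additional positive identified, parallel to the yield measure in section 6.2. State the numerator (cost per attendee) explicitly, and leave the section 2.6 comparison of average cost per positive in place alongside it.

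Do not borrow the word *newly* from Aim 2 unless the Aim 1 data can separate new from known positives. The Schema describes the Aim 1 population as not already known to be positive, but the criteria in 2.2.1 and 2.2.2 do not exclude known positives, and 2.4.3 only advises them to opt out of the self-test.

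The cost is one clause and a short definition. The count of positives per arm is already needed for the section 2.6 comparison, so randomization, sample size and data collection do not change.

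### Section 2.6.2 uses a cost as a measure of effectiveness, and, separately, the only range planned for cost-effectiveness in either aim reflects kit price alone

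*Combined protocol and SAP*

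**What the plan says.** Section 2.1.1 lists as a primary objective of Aim 1: "To determine whether group self-testing in waiting areas of OPD and STI clinics is cost-effective compared to optimized standard of care using PITC". Section 3.1.1 has the matching objective for Aim 2. Section 2.6 compares the arms on average cost per HIV-positive person identified, "with the primary comparison of optimized standard of care compared to group self-testing".

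Section 2.6.2 gives two measures of effectiveness: "the proportion of individuals tested for HIV and the cost per HIV-positive individual identified". It continues: "We will calculate the difference in cost divided by the difference in effectiveness between study arms for both measures of effectiveness". Because the kit price is uncertain, "we will conduct a sensitivity analysis where all costs and outcomes remain constant, and the price of self-tests alone is varied". The product is described in these words: "This analysis will then provide a plausible range of the cost-effectiveness of self-testing".

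Aim 2 section 6.2 has the same price analysis and ends alike: "This analysis will then provide a plausible range of the cost-effectiveness of partner self-testing". Its second measure, however, is yield, meaning HIV-positive partners newly found.

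On dispersion, section 2.6.1 says: "Costs will be reported as means (standard deviations) and medians (IQRs) in U.S. dollars". Section 6.1 repeats this for Aim 2. The hierarchical models in sections 2.5.1 and 3.5.1.1 deal with testing and positivity, not with costs or the ratio.

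**The concern.** The two defects are independent, and either would stand without the other.

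1. A cost is used as an effect. An incremental ratio needs a health or service effect in its denominator. If the denominator is a difference in cost per case, the money cancels and the quotient cannot be read as the price of anything. An analyst who follows section 2.6.2 literally will report a second ratio with no interpretation.

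2. A price range stands in for the range of cost-effectiveness. A one-way analysis of kit price answers a fair question about price. It does not show how well five facilities per arm estimate the difference in effect or in cost. Since it is the only range planned and is labelled as the plausible one, a primary conclusion could look more settled than the data allow. The risk is greatest for cost per positive, which is the quantity section 2.6 uses for its primary economic comparison.

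**Working it through.** **Defect 1: units.** Let c be cost per attendee and e positives per attendee, with subscript 2 for optimized standard of care and 3 for self-testing. The ratio as written is (c3 − c2) / (c3/e3 − c2/e2), which is dollars over dollars per positive. The ratio wanted is (c3 − c2) / (e3 − e2). The documents give no costs, so the figures here are assumed for illustration: $0.50 and $2.00 per attendee.
- 6 and 18 positives per 1,000: costs per positive are $83.33 and $111.11. As written, 1.50 / 27.78 = 0.054. Proper ratio, 1.50 / 0.012 = $125 per additional positive.
- 4 and 18 positives per 1,000: costs per positive are $125 and $111.11. As written, 1.50 / (−13.89) = −0.108. Proper ratio, 1.50 / 0.014 = $107.

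In the second case self-testing finds more positives at a lower proper ratio, yet the ratio as written changes sign.

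**Defect 2: sampling error left out.** The economic sections state no figure to reproduce, so the method was first tried on the power statements. The design effect is DE = 1 + (m − 1) × ICC and the effective size is n/DE.
- Aim 1 (section 2.5.1: 5 clusters of 1,000 per arm, ICC 0.004): DE = 4.996 and effective size 1,001 per arm. Power for 5% versus 10% is 98.9% (normal) or 96.0% (t, 8 df), and for 10% versus 60% about 100%. The stated figure of at least 95% is reproduced.
- Aim 2 (section 3.5.1.1: 600 per arm, 20% versus 40%, ICC 0.004): power comes out above 99.9%, against 89% stated. An ICC of 0.04 gives 88.9%. That discrepancy is a separate matter; the results below use the stated 0.004.

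Then, for effects p2 and p3 with difference d:

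SE = √{[p2(1 − p2) + p3(1 − p3)] × DE / n}; limits d ± 2.306 × SE (t, 8 df for ten facilities).

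With the cost difference fixed, the ratio runs from d/upper to d/lower times its estimate.

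- Aim 1, per additional person tested: 10% versus 60%. SE = √(0.33 × 4.996/5,000) = 0.0182; limits 0.458 to 0.542; ratio **0.92 to 1.09 times**.
- Aim 2, per additional partner tested, 600 per arm: DE = 1 + 119 × 0.004 = 1.476; SE = √(0.40 × 1.476/600) = 0.0314; limits 0.128 to 0.272; ratio **0.73 to 1.57 times**.
- Aim 2 at the schema's 2,500 per arm: DE = 1 + 499 × 0.004 = 2.996; SE = √(0.40 × 2.996/2,500) = 0.0219; limits 0.150 to 0.250; ratio **0.80 to 1.34 times**.
- Aim 1, per additional positive, assuming 3% positivity among those tested in both arms: p2 = 0.10 × 0.03 = 0.003, p3 = 0.60 × 0.03 = 0.018, d = 15 per 1,000. SE = √(0.020667 × 4.996/5,000) = 0.00454; limits 4.5 to 25.5 per 1,000; ratio **0.59 to 3.3 times**.

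The last result rests on two assumptions, since the documents give neither positivity nor an ICC for case finding:
- Positivity, at ICC 0.004: 5% in both arms gives 0.65 to 2.17 times. With 6% (optimized) versus 3% (self-testing) it is 0.52 to 15 times. With 8% versus 3% the lower limit of the difference is −1.7 per 1,000, so there is no finite upper limit.
- Between-facility variation, at 3% positivity: a coefficient of variation of 0.25 gives 0.69 to 1.79 times, and 0.5 gives about 0.59 to 3.3 times.

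**The case against.** The strongest reply is that section 2.6.2 offers the price analysis because the price is uncertain, and holding all else constant is what a one-way analysis means. It does not prohibit intervals elsewhere. That stands. A reader might infer that the plan excludes sampling error by rule, or that the economic result can have no valid uncertainty. The text supports neither: it is silent on an interval and gives the price range too broad a label.

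It can also be said that the cost-as-effect phrase is a slip. Section 2.6 already plans a coherent comparison of cost per positive, and Aim 2 uses yield. Probably so, but section 2.6.2 applies the division to both measures explicitly, so the text needs correcting. A reader might also link the two defects and suppose that one causes the other; it does not.

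On size, three cautions hold.
- For Aim 1 cost per additional person tested, the omitted error is only about 9% either way at the planned ICC.
- A reader might carry an ICC of 0.04 over to case finding and conclude that the Aim 1 ratio has no upper limit. For a 0.3% outcome that ICC implies a between-facility coefficient of variation of √(0.04 × 0.997/0.003) = 3.65, which is not credible. Even 0.004 implies 1.15 in that arm, though the self-testing arm supplies most of the variance and there it implies √(0.004 × 0.982/0.018) = 0.47.
- Costs probably rise with the number of tests, so fixing the cost difference is a simplification. This is why costs and effects should be analysed jointly.

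**Conclusion.** Both defects hold. The second measure in section 2.6.2 is wrong as written and yields a ratio without meaning. The price-only range in sections 2.6.2 and 6.2 is legitimate for price but is mislabelled, and nothing in the plan carries sampling error into the cost-effectiveness ratio: the cost SDs and IQRs are descriptive, and the outcome models do not cover cost.

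At ICC 0.004 the omission is minor for Aim 1 cost per additional person tested, moderate for Aim 2 cost per additional partner tested and large for Aim 1 cost per additional positive. The first two rest on the plan's own coverage and ICC. The Aim 2 size depends on whether the 600 per arm that section 3.5.1.1 treats as a minimum or the schema's 2,500 applies. The third is conditional on assumed positivity and on borrowing the ICC from testing coverage. All the ranges hold the cost difference fixed, so they isolate the effect side and do not forecast the final interval.

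**What to change.** - In section 2.6.2, replace the second measure with HIV-positive individuals identified, as a number or as a proportion of attendees, in line with yield in Aim 2 section 6.2. This changes one phrase.
- In both sections, call the price analysis the range over kit price.
- At each kit price, add an interval for the comparison of self-testing with optimized standard of care. Build it from facility-level mean costs and effects taken jointly: Fieller limits, or net benefit over a stated range of willingness to pay, with 8 df. If the Fieller interval is unbounded, report it so.
- Prefer facility means to client-level resampling. Aim 1 confirmed positivity comes from anonymized registers, so pairing each client's cost with the outcome is doubtful, and resampling only five facilities per arm understates the between-facility variance by a factor of about 4/5.

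A cost-effectiveness plane and acceptability curve are optional. The cost is a little more analysis work and a wider reported range. Design, sample size and data collection need not change, since sections 2.6.1 and 6.1 already plan resource quantities for each study patient.
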